## CLINICAL PROTOCOL

SPONSOR: ZMS

PROTOCOL: ZMS-1500-Pa2023

## 5 STUDY PROCEDURE

Figure 1: Procedure Overview

### 5.1 ENROLLMENT

A subject will be considered enrolled in the study after providing written informed consent. Subjects will only be eligible to participate in the study if they have consented to undergo a 1-unit whole blood draw procedure. Enrollment in the study is anticipated to take a subject approximately 60-90 minutes.

#### 5.1.1 INFORMED CONSENT

The Investigator or qualified designated study personnel will complete the Informed Consent process before any study procedures may occur. The subject will be provided an IRB-approved version of the Informed Consent Form (ICF). The subject will have an ample amount of time to read the ICF and ask questions before providing written consent. The subject will receive a signed copy of the ICF. The Investigator or qualified designated study personnel will record that consent was obtained prior to performing study procedures.

A subject who has signed an Informed Consent but is found to ultimately not meet eligibility criteria prior to the blood draw will be classified as "Consent Ineligible". There are no follow-up or reporting requirements for consent ineligible subjects. They do not count towards the enrollment ceiling and will not be used for analysis of the endpoints. The original signed Informed Consent must be maintained in the center's patient file.

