## CLINICAL PROTOCOL

SPONSOR: ZMS

PROTOCOL: ZMS-1500-Pa2023

Baseline hemoglobin will be collected as part of a standard blood draw procedure via a finger stick (or per standard of care for the site). Subjects that are unable to proceed with the blood donation due to their baseline hemoglobin level will be consent ineligible.

Following demographic and enrollment data collection and PRIOR to blood donation, all subjects will be connected to the CM-1500 per the Instructions for Use. Designated study personnel must ensure that the subject ID number and gender is entered for each subject prior to starting a new monitoring session.

The CM-1500 will be connected to the subject's left side of the body. Once the needle stick has been completed but the line is clamped to prevent premature blood draw, the subject's chair should be adjusted to the position assigned upon enrollment. The monitoring session should then start with the subject placed in the designated position for a minimum of ten (10) minutes before the baseline measurements will be recorded. Just prior to the blood draw, a skin temperature recording should occur on the left dorsal wrist.

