### 5.4 ADVERSE EVENTS

Adverse Events (AE), Serious Adverse Events (SAE), or Unanticipated Adverse Device Effect (UADE) that occur after informed consent and before completion of the study will be recorded. SAE's may require follow-up contact via a telephone call, depending on the nature of the SAE.

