## 7 RISKS & BENEFITS

### 7.1 RISK DETERMINATION & REDUCTION

This study is determined to be non-significant risk. An Investigational Device Exemption will not be submitted based on this determination.

Study subjects are subject to risk no greater than or similar to risks associated with undergoing a standard blood donation. The use of the CM-1500 does not meet the definition of significant risk under 21CRF 812.3 (m). All adverse events will be recorded and analyzed to evaluate their significance. Possible risks may include:

- [Possible, Rare] Skin irritation could occur from the electrodes
- [Possible, Mild] Discomfort could occur due to lying in a supine position for duration of the donation procedure.

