### 8.2 SAFETY REPORTING

Safety reporting begins at the time of signed Informed Consent and ends at subject study completion.

Investigators shall submit to the Sponsor a report of any AE's or SAE's that occur during the study within five (5) working days but no later than ten (10) days after the Investigator learns of the event.

Investigators shall submit to the Sponsor a report of any UADE(s) that occur during the study as soon as possible but no later than five (5) working days after the Investigator learns of the effect. Sponsors will evaluate UADE's.

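### Section 5.1.1 waives reporting for Consent Ineligible subjects without excepting safety events, while Sections 5.4 and 8.2 require adverse events to be captured from signed consent

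*Combined protocol and SAP*

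**What the plan says.** Section 5.1.1 defines a Consent Ineligible subject as someone who signed consent but is then found, before the blood draw, not to meet the eligibility criteria. It says of this group: "There are no follow-up or reporting requirements for consent ineligible subjects". It goes on to say that they do not count towards the enrollment ceiling and are not used in the endpoint analysis. Section 5.2 gives one explicit route into the group: "Subjects that are unable to proceed with the blood donation due to their baseline hemoglobin level will be consent ineligible".

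The safety text has no such exception:

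- Section 5.4 covers AEs, SAEs and UADEs "that occur after informed consent and before completion of the study will be recorded", and adds that an SAE may need telephone follow-up.
- Section 8.2: "Safety reporting begins at the time of signed Informed Consent and ends at subject study completion". It continues: "Investigators shall submit to the Sponsor a report of any AE's or SAE's that occur during the study".
- Section 7.1: "All adverse events will be recorded and analyzed to evaluate their significance". The same section later commits to reporting all of them to the sponsor.

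Section 5.1 places these people inside the study: "A subject will be considered enrolled in the study after providing written informed consent".

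**The concern.** Sections 5.1.1 and 8.2 both speak of reporting, and for the same person in the same period they give opposite answers on whether it is required. No section says which prevails. If a subject has, say, a skin reaction to the electrodes and is then found ineligible, a coordinator reading 5.1.1 would conclude that no form is due, and one reading 8.2 would conclude that it is.

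What is at stake is complete safety capture in people who have had study procedures. Section 8.2.1 makes the sponsor responsible for IRB and regulatory reporting, and the sponsor cannot meet that duty for events it never receives. The safety assessment in Section 8 is a review and summary of AEs, so an event left off the forms is also missing from that summary.

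**Working it through.** No arithmetic applies: the plan states no figure on this point. The check is to set the provisions side by side and ask whether a real case falls under both.

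**1. When each rule applies.**

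| Provision | Starts | Ends | Exception for Consent Ineligible |
|---|---|---|---|
| 5.1.1 waiver | Once found ineligible, at any time before the draw | Not stated | It is the exception; safety is not carved out |
| 5.4 recording | Informed consent | Study completion | None |
| 8.2 reporting | Signed consent | Subject study completion | None |
| 7.1 commitment | Not stated | Not stated | None |

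The waiver and Sections 5.4 and 8.2 overlap for any event between signed consent and classification as Consent Ineligible.

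**2. Whether anything can happen in the overlap.** Sections 5.2 and 5.3 place these steps after consent and before the draw: the hemoglobin check (finger stick or site standard), connection to the CM-1500, needle placement with the line clamped, adjustment of the chair, and at least 10 minutes of monitoring in position. Section 7.1 itself names skin irritation from the electrodes as a possible risk.

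**3. Whether ineligibility can surface after exposure has begun.**

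- Hemoglobin (5.2): yes, after the finger stick. In the order of the text this comes before device connection.
- Exclusion E.5 (body hair that prevents adequate electrode application): this may become clear only when the electrodes are applied.
- Pregnancy, amputation, dextrocardia and pacemaker (E.1 to E.4): these can be known without any study procedure.
- Inclusion I.4 (eligible to donate): this could in principle be judged again up to the draw, including after needle placement.

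Exposure before classification is therefore certain for the finger-stick route, plausible at device connection, and possible but less likely after needle placement.

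**4. Whether another section resolves the conflict or recovers the event.**

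- Section 8.1.1 says that all AEs related to the donation procedure will be recorded and reported. This supports 8.2 but does not mention the waiver.
- Section 9.2 limits the analyses to eligible subjects connected to the device, and no separate safety set is described. An event that was reported would still have no stated place in the outputs.
- Section 8.2 stops at subject completion, which Section 5.5 defines by the end of the monitoring session and removal of the device. A subject ruled out at the hemoglobin check reaches neither, so the end of the reporting window is undefined for that person.

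The overlap is real, and no section reconciles it.

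**The case against.** The strongest reply is that 5.1.1 was meant as a screen-failure accounting rule. The sentence sits next to the enrollment ceiling and the exclusion from endpoint analysis, and it waives requirements without forbidding anything. A site that reports these events under 8.2 complies with both sections. Several safety passages say any or all AEs, so a careful site would probably report. All of that is fair, and it means that lost events are a possible result of relying on 5.1.1, not something the plan sets out to do. It does not remove the conflict, because the sentence makes no distinction between endpoint data and safety data.

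Three stronger readings are tempting, and the documents do not support them.

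- *Loss of events would be selective, because subjects who react early are the ones reclassified.* No eligibility criterion names an adverse event. A subject who reacts at the needle stick fits withdrawal criterion W.3 in Section 4.4 at least as well, and Table 2 lists early withdrawal as an action taken for an AE. I.4 could be stretched to cover such a case, and no rule chooses between the two labels, but that does not establish a bias.
- *The exploratory AE objective in Section 2.1 would be damaged.* That objective relates AEs to demographics, parameter changes and timing. Section 2.4 defines change as after draw minus before draw, and these subjects have no draw. Little would be lost.
- *Section 7.1 also requires capture from consent.* It covers all AEs but gives no start time. Only 5.4 and 8.2 do.

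**Conclusion.** The point holds as an internal inconsistency with a safety consequence: a site that relies on 5.1.1 can fail to report an event that 8.2 requires. It should be corrected before sites are trained. No endpoint estimate is affected, since these subjects are already outside the endpoint analysis.

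The number of people affected is not given and is probably small. A reader might try to size it by assuming a reclassification rate. With an assumed 5% to 15% of consented subjects and 60 retained, that gives 60 × 0.05/0.95 = 3.2 to 60 × 0.15/0.85 = 10.6 people. At the minimum of 20 per position, so 40 retained, it gives 40 × 0.05/0.95 = 2.1 to 40 × 0.15/0.85 = 7.1. I place no weight on these figures. The rate has no basis in the documents, and the figures count people, not events. Nor can all of these people be called exposed to the device, because the only reclassification step that the protocol describes comes before connection in the text.

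The conclusion rests on reading 5.1.1 as written. If the sponsor intended a waiver of non-safety data only, the fix simply states that intention.

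**What to change.** Reconcile 5.1.1 with 5.4 and 8.2:

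1. In 5.1.1, limit the waiver to endpoint data and non-safety follow-up. State that AEs, SAEs and UADEs from signed consent until the subject is classified Consent Ineligible and leaves are recorded and reported under 5.4 and 8.2, including any SAE follow-up under 5.4. This also supplies the missing end of the window for these subjects.
2. State that an AE that stops participation is classified as a withdrawal under Section 4.4, W.3, and is still reported, so that capture does not depend on which label a site chooses.
3. List events in Consent Ineligible subjects separately in the safety summary, and note in 9.2 that this listing is not restricted to eligible subjects.

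The cost is a few sentences of text, one extra listing and a few more AE forms for people who are not otherwise analyzed. No procedure is added and no endpoint analysis changes.

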### 5.2 DEMOGRAPHIC AND BASELINE DATA

Demographic and enrollment data collection will include capturing health screening data on a case report form (CRF). These data will include but are not limited to skin tone, smoking history, a blood donation anxiety questionnaire, blood donation history, and if subjects are currently taking any medications or supplements that could impact their physiological response to the blood draw procedure. Female subjects will self-report they are not currently pregnant or have been pregnant in the previous six (6) weeks.

## CLINICAL PROTOCOL

SPONSOR: ZMS

PROTOCOL: ZMS-1500-Pa2023

Baseline hemoglobin will be collected as part of a standard blood draw procedure via a finger stick (or per standard of care for the site). Subjects that are unable to proceed with the blood donation due to their baseline hemoglobin level will be consent ineligible.

Following demographic and enrollment data collection and PRIOR to blood donation, all subjects will be connected to the CM-1500 per the Instructions for Use. Designated study personnel must ensure that the subject ID number and gender is entered for each subject prior to starting a new monitoring session.

The CM-1500 will be connected to the subject's left side of the body. Once the needle stick has been completed but the line is clamped to prevent premature blood draw, the subject's chair should be adjusted to the position assigned upon enrollment. The monitoring session should then start with the subject placed in the designated position for a minimum of ten (10) minutes before the baseline measurements will be recorded. Just prior to the blood draw, a skin temperature recording should occur on the left dorsal wrist.

### 5.3 SUBJECT PARTICIPATION

Subjects will proceed with the blood draw procedure wearing the CM-1500 on the left arm. For this protocol, blood draws can only occur on the right arm. Subjects will remain in their assigned position for the entirety of the procedure unless position change is required in response to a subject reaction. Immediately prior to the start of the blood donation procedure, the Investigator or designated study personnel will press the 'MARK EVENT' button on the CM-1500 and record the local time on the CRF which will signify the start of the procedure on the device.

The Investigator or designated study personnel will monitor the subject per standard of care throughout the procedure and record any adverse events noted. Total amount of blood collected will vary per subject based upon their estimated blood volume, and the final amount drawn will be recorded.

Immediately following completion of the blood donation, the Investigator or designated study personnel should press 'MARK EVENT' on the CM-1500 and record the local time on the CRF. Skin temperature from the left dorsal wrist should again be measured at this time.

Subjects will remain connected to the CM-1500 for at least ten (10) minutes following the donation procedure. Following the 10-minute post-donation monitoring period, subjects will be disconnected from the study device, and study participation will be complete.

### 5.4 ADVERSE EVENTS

Adverse Events (AE), Serious Adverse Events (SAE), or Unanticipated Adverse Device Effect (UADE) that occur after informed consent and before completion of the study will be recorded. SAE's may require follow-up contact via a telephone call, depending on the nature of the SAE.

### 5.5 SUBJECT COMPLETION

Subjects' participation in the study will be considered complete once the monitoring session has ended and the device has been removed.

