### 8.1 SAFETY DEFINITIONS

#### 8.1.1 ADVERSE EVENT (AE)

An Adverse Event (AE) is defined as any untoward medical occurrence, whether or not related to the study device or study procedure. AE's are characterized by grading, actions taken, relationship to donation or study procedure, and outcome. These definitions are in the corresponding tables below. All adverse events related to the blood donation procedure will be recorded and reported in addition to those that may occur specific to the protocol-defined study procedure. All attempts should be made to ensure resolution of the adverse event upon study completion.

Table 1: Adverse Event Severity Grading

Severity	Description
Grade 1: Mild	Awareness of signs or symptoms, but they are easily tolerated
Grade 2: Moderate	Enough discomfort to cause interference with usual activity
Grade 3: Severe	Incapacitating, with the inability to work or do usual activity
Grade 4: Fatal	Subject expired/death occurred

Table 2: Adverse Events Action(s) Taken

Action Taken (Check all that apply)	Description
None	No actions were taken, observation only.
Medications	Subject required medication(s)
Other Treatment	Subject required other treatment(s)
Early Withdrawal	Adverse event led to early study withdrawal

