### 8.1.2 SERIOUS ADVERSE EVENT (SAE)

An SAE is defined as an AE that meets any of the following criteria: Fatal or life-threatening\*; requires or prolongs in-subject hospitalization\*\*; results in persistent or significant disability/incapacity; congenital anomaly/birth defect; important medical event. An event's severity grading, action(s) taken, relationship to the donation or study procedure, and the outcome will all be used for SAE's.

\*Life-threatening is defined as an event in which the subject was at risk of death at the time of the event. It does not refer to an event that hypothetically may have caused death if it was more severe.

\*\*In-subject hospitalization is defined as an event in which the subject was admitted to the hospital for one or more days, even if released on the same day or an emergency room visit, which results in admission to the hospital. Emergency room visits that do not result in admission to the hospital should be evaluated for one of the other serious outcomes criteria.

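### Safety reporting stops at device removal with no scheduled skin check, so skin findings rely on incidental notice and reactions starting before release from the site go unrecorded

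*Combined protocol and SAP*

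**What the plan says.** Section 8.2 sets the reporting window: "Safety reporting begins at the time of signed Informed Consent and ends at subject study completion". Section 5.4 records events "that occur after informed consent and before completion of the study will be recorded".

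Completion for a subject is defined twice, consistently. Section 5.5 says: "Subjects' participation in the study will be considered complete once the monitoring session has ended and the device has been removed". Section 5.3 first sets a minimum period after the draw ("Subjects will remain connected to the CM-1500 for at least ten (10) minutes following the donation procedure"), after which "subjects will be disconnected from the study device, and study participation will be complete".

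Section 7.1 lists two possible risks. One comes from the device: "Skin irritation could occur from the electrodes". The other is discomfort from lying supine. The same section undertakes to record and analyse all adverse events, and 8.1.1 undertakes to record and report every event related to the donation. Section 8.1.1 adds: "All attempts should be made to ensure resolution of the adverse event upon study completion". Table 4 words its outcome categories for resolved, persisting and unknown events as status at study completion. The only later contact mentioned is a possible telephone call for serious events (5.4).

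**The concern.** Section 8 makes the review and summary of adverse events the whole safety assessment, so the rule on when recording stops decides what that summary can contain. Here the rule stops at the step that uncovers the skin under the electrodes, and nobody is asked to look. It also stops while the subject may still be at the site after giving about 500 mL of blood.

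Two uses of the data are touched. The first is the undertaking in 8.1.1 on donation-related events, which the 8.2 cutoff narrows. The second is the exploratory objective in 2.1 that relates adverse events to demographics, parameter changes and the time at which events occurred. A cutoff at removal truncates that timing variable.

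**Working it through.** The protocol states no safety rate or precision target to reproduce, and 9.1 bases the sample size on clinical judgment. The check is a comparison of definitions.

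1. **End of the window.** Reporting ends at subject study completion (8.2). Completion is the end of the session with the device off (5.5), and 5.3 treats disconnection and completion as one step. Planned observation after removal is 0 minutes.

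2. **Length after the draw.** The period is at least 10 minutes (5.3). This is a floor with no upper limit. The whole visit is expected to take about 60 to 90 minutes (5.1).

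3. **Scheduled skin check.** The pre-draw steps (5.2), the draw and post-draw steps (5.3) and the adverse event sections (5.4, 8.1) contain none. The wrist measurements in 5.2 and 5.3 are temperature readings.

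4. **What is in and what is out.** Under 5.4 an event counts by when it occurs.
   - Irritation that develops while the electrodes are worn is in. The skin is covered until removal, so unless the subject complains, its recording depends on staff noticing it as the electrodes come off.
   - Irritation or a donation reaction that begins after removal and before the subject leaves is out.
   - For a subject withdrawn because of an adverse event (criterion W.3 in 4.4), no separate end point is given, so the same rule closes reporting when the device comes off.

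5. **Outcome of an ongoing event.** Section 5.4 refers to completion of the study, 8.1.1 and Table 4 to study completion, and 8.2 to subject study completion.
   - Read at subject level, a non-serious event still present at removal is classified then and not updated.
   - Read at trial level, the outcome could be updated later, but no contact is planned through which the site would learn it.
   - Neither reading gives the site a workable way to pursue the resolution that 8.1.1 asks for. For serious events, the possible call has no stated timing and no rule for updating Table 4.

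**The case against.** The strongest reply is that nothing tells staff to ignore what they see. Removal is itself a study step, done by trained personnel who must record adverse events, and the reporting deadlines in 8.2 and 8.2.1 run from when the investigator learns of an event. Irritation from worn electrodes occurs inside the window, and itching or burning can be reported while the device is on. This stands. A reader might infer that the window shuts out essentially all skin irritation; the documents do not support that.

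Other stronger readings also go too far:

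- **Getting up.** A reader might infer that rising from the chair is certainly unobserved. Section 5.3 holds the assigned position for the procedure, but for the following 10 minutes it requires only that subjects stay connected. When they get up is not stated.
- **Frozen outcomes.** A reader might infer that every unresolved event is fixed about 10 minutes after donation. Ten minutes is a minimum, the completion wording may refer to the whole trial, and serious events may prompt a call.
- **Serious events.** Criteria such as "requires or prolongs in-subject hospitalization" are hard to meet in so short a period, but 8.1.2 also includes life-threatening and important medical events, which can occur during a donation. The documents do not show that the optional call must become mandatory.
- **Risk determination.** Section 7.1 makes its non-significant-risk determination in advance; it does not rest on this study's event counts.
- **Upper bounds.** A confidence bound for a hypothetical zero count would not measure how many events the window misses.

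It is also fair to say that this is a feasibility study of a cleared device, that no endpoint in 2.4 is a safety endpoint, and that 7.1 labels irritation as rare. These points limit the importance of the gap without closing it.

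**Conclusion.** The point holds as a minor one. Reporting ends at removal, no skin check is scheduled around it, and no follow-up is planned for ongoing non-serious events. The effect is confined to the adverse event summary and the exploratory work on event timing, in up to 60 subjects. The number of events affected cannot be estimated from the documents.

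The conclusion assumes that completion in 8.2 is meant per subject, as 5.3 and 5.5 indicate, and that some time passes between removal and leaving the site; the protocol does not give that interval. Figure 1 was not readable in the text reviewed, and the CRF and Instructions for Use are separate documents. If one of them already contains a skin item after removal, that part of the point reduces to citing it in 5.3.

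**What to change.** - In 5.3, 5.5 and 8.2, end the adverse event reporting window when the subject is released from the site, and state that the same end point applies to withdrawn subjects.
- In 5.3, add a yes/no CRF item, completed after removal, for skin findings at the electrode and wrist-strap sites.
- Reconcile the completion terms in 5.4, 8.1.1, Table 4 and 8.2, so that the Table 4 outcome for an ongoing event is recorded at last contact.

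The cost is one CRF line, a few minutes of existing staff time per subject, and a few more mild adverse events in the report. Endpoints, sample size and study procedures before removal are unchanged. Irritation that first appears after the subject has left would still not be captured, and the report should describe the window in those terms.
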